12.3 Women and Minorities

This study is being conducted by the AMC, a NCI-sponsored clinical trials consortium. As part of the AMC's contractual obligations, each participating site within the AMC and the AMC as a whole is required to assure that the participation of women and minority subjects reflects the percentage representation of these populations in their geographic region. As such, it is expected that the representation of subjects on this trial will reflect the constitution of the respective populations.

12.4 Subject Confidentiality

To maintain confidentiality, all laboratory specimens, evaluation forms, reports and other records will be identified by a coded number only and de-identified from the subject. Clinical information will not be released without written permission of the subject, except as necessary for monitoring by the AMC or the NCI.

12.5 Study Discontinuation

This study may be discontinued at any time by the NCI, the AMC, or the Office for Human Research Protections (ORHP).

APPENDIX I: SCHEDULE OF EVENTS

The following observations and tests are to be performed and recorded on the appropriate form(s):

Tests and Observations	Prior to Entry	Weekly During Chemo-Radiation	Chemo-Radiation Therapy Completion or Premature Treatment Discontinuation ¹⁰	3, 6, 9, and 12 Month Follow-up	After Diagnosis of Recurrence	Premature Study Discontinuation ⁶
Medical History	X ¹					
Physical exam	X ¹	X ²	X ²	X ²		X
Tumor measurements and clinical staging	X ¹					
CT scan with contrast of pelvis and abdomen	X ¹			X ³	X	X
Chest X-ray †	X ¹				X	X ⁷
CD4+ T-cell count	X ¹			X ⁴	X	X ⁷
HIV viral load	X ¹			X ⁴	X	X ⁷
CBC + differential	X ⁵	X				X ⁷
Calculated creatinine clearance	X ⁵	X				X ⁷
SGOT, SGPT, alkaline phosphatase, bilirubin	X ⁵					X ⁷
Electrolytes (Na, K, Cl, Mg)	X ⁵	X				
Serum or urine pregnancy test *	X ⁵					X ⁸
Review of interim medical history		X	X	X ⁸	X	X
Slides for central pathology review	X ⁵					
ART Adherence		X	X	X		
Cytoscopy, IVP	X ^{5,+}					
Anal and cervical swabs for HPV-associated disease research	X ⁵		X ⁹			X
Serum for HPV-serology	X ⁵		X ⁹		X	X

X¹ Must be obtained within 28 days prior to initiating protocol therapy

X² At day 22 prior to treatment, at treatment discontinuation, and every 3 months for 1 year.

X³ CT with contrast of abdomen and pelvis to be done prior to study entry, 6 months +/- 4 weeks and 12 months +/- 4 weeks after concomitant chemoradiotherapy. Can perform CT without contrast only if recent creatinine ≥ 1.5 mg/dL (within 4 weeks of scan).

X⁴ Every 6 months while on protocol

X⁵ Must be obtained within 14 days prior to initiating protocol therapy. If ANC $\leq 1,500/\text{mm}^3$ ($1.5 \times 10^9/\text{L}$) or platelets $\leq 50,000/\text{mm}^3$ ($50 \times 10^9/\text{L}$), repeat twice per week until over these values or subject off trial.

X⁶ Evaluations should be performed whenever possible, preferably at the time of or up to 1 month after withdrawal from study.

- X⁷ Tests are required if not done within the last 3 months.
- X⁸ Every 3 months for 1 year.
- X⁹ Anal and cervical swabs and serum for HPV-associated disease research will be collected on the final day of chemo-radiation therapy or within 4 weeks following the final chemo-radiation therapy.
- X¹⁰ Assessments must be completed within 7 days of the completion of chemo-radiation therapy. This visit is required for all participants and refers to both to scheduled completion of treatment and premature treatment discontinuation
- * Excludes participants who have had a bilateral tubal ligation prior to study entry or who are postmenopausal.
- † Chest CT scan with contrast may be substituted for chest x-ray
- ⁺ Cystoscopy and IVP are not required for eligibility per protocol, but if the enrolling physician feels they are clinically indicated for accurate staging, they should be done according to local standard of care. The costs of these procedures will not be borne by the study budget.

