3.1 Inclusion Criteria

- 3.1.1 Participants (who have been adequately clinically staged by standard clinical guidelines) with primary, untreated, histologically-confirmed, documented invasive squamous cell carcinoma, adenocarcinoma, or adenosquamous carcinoma of the uterine cervix, FIGO stages IB2, IIA, IIB, IIIA, IIIB, and IVA. (Stage IIA tumors must be greater than 4 cm.)
- 3.1.2 HIV-1 infection, documented by any licensed rapid HIV test or HIV enzyme or chemiluminescence immunoassay (E/CIA) test kit at any time prior to study entry and confirmed by a licensed Western blot or a second antibody test by a method other than the initial rapid HIV and/or E/CIA, or by HIV-1 antigen, plasma HIV-1 RNA viral load.

NOTE: The term “licensed” refers to a U.S FDA-approved kit or for sites located in countries other than the United States, a kit that has been certified or licensed by an oversight body within that country and validated internally.

WHO (World Health Organization) and CDC (Centers for Disease Control and Prevention) guidelines mandate that confirmation of the initial test result must use a test that is different from the one used for the initial assessment. A reactive initial rapid test should be confirmed by either another type of rapid assay or an E/CIA that is based on a different antigen preparation and/or different test principle (e.g., indirect versus competitive), or a Western blot or a plasma HIV-1 RNA viral load.

- 3.1.3 The following laboratory tests within 14 days of study enrollment:
 - Hemoglobin \geq 10 g/dL (6.2 mmol/L)
 - Platelet count \geq 100,000/mm³ ($100 \times 10^9/L$)
 - ANC \geq 1500/mm³ ($1.5 \times 10^9/L$) (Participants receiving transfusion, erythropoietin, or myeloid growth factor support will be eligible for this study)
 - Creatinine clearance \geq 60 mL/min (1.00 mL/s) calculated by the Cockcroft-Gault equation for women
 - AST and ALT \leq 3 X ULN
 - Total bilirubin \leq 2 X ULN unless related to antiretroviral use (e.g., atazanavir and indinavir), then the direct bilirubin must be \leq 2 X ULN

- 3.1.4 Adults, 18 years of age or older. DOB and age should be determined based on best possible information or documentation available.

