6.1.1.1 Blood/Bone Marrow (Hematologic)

Hematologic toxicity is seen infrequently unless pelvic radiation is accompanied by chemotherapy. A CBC should be obtained weekly, and if the ANC falls below $1500/\text{mm}^3$ ($1.5 \times 10^9/\text{L}$) or the platelet count drops below $100,000/\text{mm}^3$ ($100.0 \times 10^9/\text{L}$), counts should be obtained twice weekly. Treatment may proceed if $\text{ANC} > 1000/\text{mm}^3$ ($1.0 \times 10^9/\text{L}$), and platelet count $> 50,000/\text{mm}^3$ ($50.0 \times 10^9/\text{L}$).

Every effort should be made to maintain hemoglobin $\geq 10\text{g/dL}$ (6.2 mmol/L). It is up to the individual investigator's discretion as to how best to achieve this.

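### Section 6.1.1.1 and Appendix I footnote 5 set different platelet triggers (100,000 and 50,000/mm³) for twice-weekly counts, and nothing says which applies in between

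*Combined protocol and SAP*

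**What the plan says.** The relevant text of the combined protocol and SAP is as follows.

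- **Section 6.1.1.1** asks for a weekly CBC. If neutrophils (ANC) fall below 1,500/mm³ "or the platelet count drops below $100,000/\text{mm}^3", then "counts should be obtained twice weekly". It does not say when the extra counts end.

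- **Appendix I, footnote 5** opens "Must be obtained within 14 days prior to initiating protocol therapy". It goes on that with an ANC of 1,500/mm³ or lower "or platelets $\leq 50,000/\text{mm}^3", the site is to "repeat twice per week until over these values or subject off trial".

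- **Appendix I, table.** On the CBC row, marker 5 appears only in the Prior to Entry column. The cell for weekly counts during chemo-radiation carries a plain X.

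- **Section 3.1.3**, under the lead-in "The following laboratory tests within 14 days of study enrollment", requires platelets of at least 100,000/mm³ and an ANC of at least 1,500/mm³.

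- **Section 5.2.1** lists a CBC with each weekly cisplatin visit and mentions no step to more frequent counts.

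- **Section 6.1.2.1** has its own twice-weekly rule, which applies only while external radiotherapy is delayed. The delay is triggered at platelets of 50,000/mm³ or lower, or an ANC of 1,000/mm³ or lower.

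- **Section 6.2.4.1** reduces cisplatin by one level at platelets of 75,000 to 99,999/µL and holds it below 75,000/µL, using counts from the 2 days before each dose.

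No section says whether Section 6 or the schedule governs where they differ.

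**The concern.** The schedule of events is the page site staff are likely to work from, and the higher platelet trigger sits elsewhere, under expected radiation toxicity. The two pages differ by a factor of two in the platelet count that starts closer monitoring. The range between them is where cisplatin is reduced or held, and it ends just above the radiotherapy-delay level.

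At stake is how soon a site sees platelets fall further, or recover enough for treatment to resume. Section 9.1.4 evaluates safety and tolerability through dose delays, reductions and missed doses. Monitoring that varies with the page followed could therefore add between-site differences to those data that have nothing to do with the regimen.

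**Working it through.** The plan gives no figure to reproduce here. The check compares the two rules across the platelet range and then looks at each reading of the footnote.

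**Step 1. Count frequency by platelet value (ANC above its own trigger, footnote read as an on-treatment rule).**

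| Platelets/mm³ | Section 6.1.1.1 | Appendix I footnote 5 | Agree? |
|---|---|---|---|
| 50,000 or lower | twice weekly | twice weekly | yes |
| 50,001 to 99,999 | twice weekly | weekly | **no** |
| 100,000 or higher | weekly | weekly | yes |

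For ANC, one rule is below 1,500 and the other is 1,500 or lower, so they part only at exactly 1,500.

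**Step 2. Size within the band.** Twice-weekly sampling of a 7-day week leaves gaps of 3 and 4 days; weekly sampling leaves 7. A woman at 60,000/mm³ would have her next count in about 3 to 4 days under 6.1.1.1 and in 7 days under the footnote, a difference of 7 − 4 = 3 to 7 − 3 = 4 days.

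**Step 3. The two readings of the footnote.**

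- *On-treatment rule.* The closing words about a subject leaving the trial point this way. Footnote and 6.1.1.1 then contradict each other across the whole band. The stop conditions differ too: the footnote ends repeats once platelets exceed 50,000, while 6.1.1.1 states no end.
- *Screening rule.* The marker's position and the opening clause point this way. The ANC value then sits at the eligibility minimum, but the platelet value is half of it (50,000 against 100,000). Repeats would end just above 50,000, with the woman still ineligible, and a screening count of 50,001 to 99,999 would prompt no repeat. The schedule would then show weekly on-treatment counts only, as Section 5.2.1 does, without the 6.1.1.1 escalation.

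Section 6.1.2.1 settles neither reading, because it applies only during a radiotherapy delay and that delay starts at 50,000, below the band.

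**Step 4. Illustration of what sampling frequency can do (nadir duration is assumed).** For a low-count episode lasting *d* days that starts at random relative to the draws, the chance that at least one draw falls inside it is:

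- weekly: min(1, *d*/7)
- twice weekly: [min(*d*,3) + min(*d*,4)]/7

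| *d* (days) | Weekly | Twice weekly |
|---|---|---|
| 2 | 2/7 = 0.29 | (2+2)/7 = 0.57 |
| 3 | 3/7 = 0.43 | (3+3)/7 = 0.86 |
| 4 | 4/7 = 0.57 | (3+4)/7 = 1.00 |
| 7 | 7/7 = 1.00 | (3+4)/7 = 1.00 |

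The documents give neither a nadir duration nor a DLT rate, so these are not estimates for this trial. They show only that frequency matters for short episodes and not for long ones.

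**The case against.** The strongest defence is that footnote 5 is a screening footnote and a site can comply with both pages. A retest trigger is not an eligibility limit: a woman at 80,000 platelets is ineligible under 3.1.3 whatever the footnote says, and Section 3.0 allows no exceptions. On treatment, the schedule shows a weekly minimum and 6.1.1.1 adds to it. This stands in part, because on that reading there is no direct contradiction with 6.1.1.1. It leaves a platelet value that does not fit screening, a closing phrase that reads as an on-study instruction, and a schedule that omits the escalation.

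A second defence is that each cisplatin decision uses a count from the 2 days before the dose, on either page. That stands: the scheduled dose decision does not depend on the footnote. What can differ is how early a fall to the radiotherapy-delay level, or a recovery, is noticed between those counts.

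A reader might go further and infer that a DLT seen at a site following 6.1.1.1 would be missed at one following Appendix I, so that the run-in decision and safety tables would differ. The documents do not support that. Weekly counts continue on either page. Section 6.2.4.1 writes grade 4 nadir thrombocytopenia as platelets of 10,000 or lower. To be missed because of this discrepancy, a count would have to read 50,001 to 99,999 at one weekly draw, drop to 10,000 or lower, and rise above that before the next. Any draw at 50,000 or lower puts both pages on twice-weekly counts. The neutrophil triggers agree except at exactly 1,500, and the formal DLT rule in 6.2.2 covers only the CD4 ≤200/mm³ run-in, with three to six women per dose level.

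**Conclusion.** The inconsistency is real and lies in current text. Its firm extent is the platelet band 50,001 to 99,999/mm³, where the next count may be about 3 to 4 days or 7 days away depending on the page followed. The contradiction is direct if footnote 5 is an on-treatment rule. If it is a screening rule, what remains is a misfit with the eligibility minimum and a missing escalation in the schedule. Either way the text needs reconciling, and because the threshold drives safety monitoring this is more than a clerical matter.

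The consequence is that detection of a further fall or of recovery may differ by site. An effect on DLT capture is possible but cannot be sized from the documents, and would be limited to thrombocytopenia in the run-in. The 3-to-4-day figure assumes evenly spread twice-weekly draws and an ANC above its own trigger.

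**What to change.** Reconcile Appendix I footnote 5 with Section 6.1.1.1, and check the result against 3.1.3 (eligibility), 5.2.1 (weekly evaluations) and 6.1.2.1 (counts during a radiotherapy delay). State one trigger and one stop condition for platelets and one of each for ANC, including what happens at the boundary value. Attach the footnote to the column it is meant for: the weekly chemo-radiation CBC cell if it is an on-treatment rule, or the pre-entry cell if it is a screening rule. In the latter case, the schedule should also carry the on-treatment escalation. Which threshold applies is for the sponsor's clinical team.

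The cost is one footnote edit and possibly a few extra blood counts at some sites. Sample size and the analysis methods are unaffected.

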APPENDIX II: PERFORMANCE STATUS SCALE

ECOG Performance Scale	
Grade	Descriptions
0	Normal activity. Fully active, able to carry out all pre-disease performance without restriction.
1	Symptoms, but ambulatory. Restricted in physically strenuous activity, but ambulatory and able to carry out work of a light or sedentary nature (e.g., light house work or office work).
2	In bed < 50% of the time. Ambulatory and capable of all self care, but unable to carry out work activities. Up and about for more than 50% of waking hours.
3	In bed >50% of the time. Capable of only limited self care. Confined to bed or chair more than 50% of waking hours.
4	100% bedridden. Completely disabled. Cannot carry on any self care. Totally confined to bed or chair.
5	Dead

APPENDIX III: THE NEW YORK HEART ASSOCIATION (NYHA) FUNCTIONAL CLASSIFICATION SCALE

NYHA Class	Symptoms
I	No symptoms and no limitation in ordinary physical activity, e.g., shortness of breath when walking, climbing stairs, etc.
II	Mild symptoms (mild shortness of breath and/or angina) and slight limitation during ordinary activity.
III	Marked limitation in activity due to symptoms, even during less-than-ordinary activity, e.g., walking short distances (20-100 m). Comfortable only at rest.
IV	Severe limitations. Experiences symptoms even while at rest. Mostly bedbound patients.

APPENDIX IV: CENTRAL PATHOLOGY REVIEW AND HANDLING OF TISSUES

Handling of Tissues

The designated pathologist at each site will collect the tissues from each patient enrolled in the protocol. One hematoxylin and eosin stained slide plus 3 unstained tissue slides must be made available for centralized pathology review. The unstained slides will be used in the event that additional stains (e.g., hematoxylin and eosin or immunohistochemical stains) are required to confirm the diagnosis (e.g., to differentiate a poorly differentiated adenocarcinoma of the uterus from a primary cervical cancer). A de-identified copy of the local pathology report must be submitted with the slides for central pathology review.

Slides for centralized pathology review should be batched at each site, and shipped via World Courier, every six months to the AMC study laboratory. Specimen storage, shipping and labeling requirements are detailed in the AMC-081 Manual of Procedures.

If any of the blank slides are not needed for central pathology review, then the slides will be destroyed.

Record of Specimens

This study will track specimens via GlobalTraceSM, a component of the AMC AdvantageEDCSM system. The GlobalTraceSM shipment manifest must accompany all specimen shipments.

Pathology Review

Specimens received from AMC will undergo histopathologic diagnosis and classification as follows:

1. H&E
2. Pathologist interpretation.
3. Additional stains for pathologic confirmation and subclassification, if needed for atypical and unusual cases, from unstained slides.

APPENDIX V: AMC DATA AND SAFETY MONITORING PLAN

Version 5.0 • January 28, 2014

Monitoring the Progress of Trials and the Safety of Participants

All AMC protocols that collect safety data follow the *National Cancer Institute (NCI), Cancer Therapy Evaluation Program (CTEP) Guidelines: Adverse Event Reporting Requirements* (<http://ctep.cancer.gov/guidelines/index.html>). All adverse events that meet the NCI's expedited reporting requirements are reported to the Investigational Drug Branch (IDB) of the NCI via the CTEP Adverse Event Reporting System (CTEP-AERS) web application. All expedited adverse event reports are also required to be submitted to the local Ethics Committee/Institutional Review Board (IRB) of the reporting institution. If NCI holds the IND or no IND is required for a study, the AMC site reports serious adverse events directly to the AMC Operations and Data Management Center (ODMC) via CTEP-AERS. In some instances, the AMC sites may report serious adverse events directly to a commercial sponsor holding the IND, who will then report the event to the AMC ODMC. Most AMC protocols require sites to report all serious adverse events via CTEP-AERS and the AMC ODMC to forward a copy of the report to the sponsor. The AMC ODMC also distributes all IND safety reports to all investigators upon receipt, and makes these reports available on the password-protected section of the AMC Operations web site. Unless an AMC protocol specifies an alternate plan for the review and submission of serious adverse events, all serious adverse events received by the AMC ODMC will be reviewed by the AMC Medical Monitor at the AMC ODMC prior to submission to NCI and the sponsor. For protocols for which the IDB does not have an assigned drug monitor to review serious adverse event reports, in the event of disagreement between the reporting physician and the AMC Medical Monitor regarding the attribution of the event to the investigational agent(s) (i.e., determination of whether the relationship is unrelated, unlikely, possible, probable, or definite), the AMC Medical Monitor will provide the final determination of the relationship.

The AMC ODMC provides listings of all reported adverse events and serious adverse events to the Protocol Chair and Co-chair(s) for review on a regular basis. The AMC ODMC compiles these events in a tabular format and posts them on the password-protected section of the AMC web site where these reports are updated nightly. The AMC web site is accessible to all AMC investigators, co-investigators, and their staff. Email notification that this information is available on the web site will be sent to all site PIs. It is the responsibility of each site to provide this information to their respective IRBs, if required by their IRB. For blinded studies, the serious adverse events are reviewed and tabulated without treatment assignment. The AMC Medical Monitor will review listings of all reported adverse events on a quarterly basis for safety concerns.

Accrual summaries for each AMC trial are updated nightly on the password-protected section of the AMC web site. The progress of each AMC trial is reviewed regularly by the Protocol Chair and also by the appropriate disease-oriented Working Group during scheduled conference calls. For Phase I dose escalation trials, dose escalation (or dose de-escalation) is based on the rules in the protocol and the Protocol Chair, AMC Medical Monitor, and Group Statistician determine whether these criteria have been met. For Phase II trials, stopping the trial for toxicity or efficacy, or suspending enrollment pending observation of responses in a multi-stage Phase II

trial, is based on meeting criteria stated in the protocol, and the Protocol Chair, AMC Medical Monitor, and Group Statistician determine whether these criteria have been met.

For Phase III trials, the AMC has formed an independent Data Safety and Monitoring Board (DSMB). Voting members of the DSMB are physicians, a statistician, and a patient advocate. All voting members are from outside the AMC. Nonvoting members are the AMC Group Statistician, the Statistician listed on the protocol, an AMC Operations Center staff member, two representatives (normally a clinician or statistician) from the Office of HIV AIDS Malignancy (OHAM) or from the Cancer Therapy Evaluation Program, Division of Cancer Treatment and Diagnosis, of the National Cancer Institute (NCI). The AMC Data Safety and Monitoring Board reviews AMC Phase III studies in accordance with the National Cancer Institute's Policy for Data Safety and Monitoring. Confidential reports of all Phase III trials are prepared by the AMC Group Statistician with support from the AMC ODMC. A written report containing the current status of each trial monitored, and when appropriate, any toxicity and outcome data, are sent to DSMB members by the AMC ODMC within the timelines specified by the AMC DSMB Charter. This report addresses specific toxicity concerns as well as concerns about the conduct of the trial. The report may contain recommendations for consideration by the DSMB concerning whether to close the trial, report the results, or continue accrual or follow-up.

The results of each DSMB meeting are summarized in a formal report sent by the DSMB Chair to the Group Chair and AMC ODMC. The DSMB report contains recommendations on whether to close each study reviewed, whether to report the results, and whether to continue accrual or follow-up. A primary recommendation (e.g., continue with no change; recommended or required modification; stop) must be included in the document. The Group Chair is then responsible for notifying the Protocol Chair and relevant Disease-oriented Working Group Chair before the recommendations of the DSMB are carried out. In the unlikely event that the Protocol Chair does not concur with the DSMB, then the NCI Division Director or designee must be informed of the reason for the disagreement. The Study Chair, relevant Disease-oriented Working Group Chair, Group Chair, DSMB Chair, and NCI Division Director or designee will be responsible for reaching a mutually acceptable decision about the study. CTEP approval of a formal amendment will be required prior to any implementation of a change to the study.

Following a DSMB meeting, a summary of the serious adverse events reported to the DSMB is posted to the AMC web site. It is each site's responsibility for conveying this information to its IRB.

Plans for Assuring Compliance with Requirements Regarding the Reporting of Adverse Events (AE)

For trials monitored by the NCI's Clinical Data Update System (CDUS), adverse event information is transmitted electronically to NCI on a quarterly basis. For trials monitored by NCI's Clinical Trials Monitoring Service (CTMS), adverse event information is transmitted electronically to NCI every two weeks.

The Protocol Chair, AMC Group Chair, and the AMC ODMC share responsibility in assuring that participating investigators comply with the protocol requirements for adverse event

reporting. All AMC investigators certify compliance with NCI and FDA requirements for adverse event reporting by signing the AMC Adherence Statement for site membership, the protocol signature page for each protocol active at the site, and Form FDA-1572 for CTEP investigator registration and IND studies sponsored by AMC investigators. Investigators are responsible for identifying and reporting all adverse events to the AMC ODMC, CTEP-AERS, and/or sponsors according to the protocol requirements, and assuring compliance with reporting to the local IRB. Protocol compliance with adverse event reporting requirements is assessed by the AMC ODMC during routine site monitoring visits by reviewing the site's source documentation.

The data entry system used for AMC studies, AdvantageEDCSM (a web-based data entry and enrollment system), is programmed to notify the site investigator, protocol chair, and AMC ODMC via email in the event that a site reports an adverse event that meets expedited reporting criteria to NCI and/or FDA. If the site does not follow with a CTEP-AERS report, the AMC ODMC contacts sites to request an expedited report. Additionally, the protocol chair, AMC ODMC, and the AMC Medical Monitor review reported adverse events on a routine basis to identify adverse events reported by sites that require expedited reporting via CTEP-AERS. The Protocol Chair, AMC Group Chair, and IND sponsors have general oversight for assuring that routine and expedited adverse reporting requirements are met by the responsible parties.

Plans for Assuring that any Action Resulting in a Temporary or Permanent Suspension of an NCI-Funded Clinical Trial is Reported to the NCI Grant Program Director Responsible for the Grant

In the event that termination of the trial or major modification to the protocol is under consideration, the Protocol Chair will convene the AMC Data Coordinator and Disease-oriented Working Group Chair by conference call to discuss the options. For Phase I and II trials, the Protocol Chair also has the option of asking the AMC DSMB to review the study. The AMC ODMC will inform the CTEP Protocol Information Office (PIO) when studies are temporarily or permanently closed. The Cancer Treatment and Evaluation Program (CTEP) of the National Cancer Institute (NCI) must approve all protocol amendments prior to distributing to the AMC sites.

Plans for Assuring Data Accuracy and Protocol Compliance

All study data for AMC clinical trials are entered directly by AMC site staff into AdvantageEDCSM. During data entry, the system performs validation checks on many fields and performs consistency checks between select fields. Range checks are placed on each field to eliminate entry of out-of-range values. Edit check programs are run on the database on a set schedule to identify and resolve inconsistencies between forms or data collected at different points in time. AMC ODMC staff routinely interacts with site staff to resolve any data problems.

In accordance with NCI guidelines, the AMC ODMC conducts monitoring visits at the AMC sites to evaluate compliance with regulatory issues, and to review data for specific cases by checking source documents. These reports are sent to the site Principal Investigator and to the NCI. In the event that major violations are identified, sites are asked to provide a plan to correct

deficiencies within 30 days. If needed, a repeat site visit is conducted. In the event that a site does not correct deficiencies in a pre-determined time frame, the AMC Executive Committee has the option of taking action against the site. Possible actions include, but are not limited to, suspending enrollment of new patients to AMC trials until deficiencies are corrected; recommending a decrease in funding to the site; and requiring specific training for site investigators or staff members.

